## 5.2 Subject Disposition

A summary table of the subject disposition by planned treatment and overall and also by strata will be prepared with number and percentage of subjects in the following categories (and sub-categories):

- Screened, randomised and exposed subjects
- Analysis sets (ITT, safety, FAS and PP analysis set)
- End of study:
  - Completed
  - Withdrawn

Sponsor:	Pharmacosmos A/S	Date:	12MAR2018
Drug/Project:	Monofer	Version:	Final 2.0
Trials:	P-Monofer-IDA-04 P-Monofer-IDA-05	Statistical Analysis Plan	

- Reason for withdrawal:
  - Adverse event
  - Screen failure
  - Withdrawal by subject
  - Lost to follow-up
  - Protocol deviation
  - Investigator decision
  - Sponsor request
  - Other

All randomised subjects by planned treatment will be used as denominator in the table.

All disposition information will be listed. Screening failures and major protocol deviations will be listed by subject. Visits outside visit window will be listed. Subjects with at least three visits outside visit window will be listed.

### 5.3 Baseline Characteristics and Demographics

Demographics and baseline characteristics consist of age, gender, race, ethnicity, height, smoking habits, and strata. Demographics and baseline characteristics will be listed and summarized using descriptive statistics, by treatment, and by treatment and strata for the safety and if different, then also for the ITT analysis set.

### 5.4 Medical History and IDA-Underlying Disease

Relevant medical history is collected. Changes in medical history will be recorded at the subsequent visits during the trials. Worsening of symptoms or diseases is recorded as AEs.

Medical history and IDA-underlying disease will be summarised and will also be listed by subject for the safety analysis set.

## 6 Exposure and Other Dosing Information

All descriptive data will be presented by treatment for the safety analysis set.

### 6.1 Exposure

Dose and compliance will be summarised. Planned and actual dose in mg, number of doses and compliance will be presented. Treatment interruptions and restarts will be listed.

Compliance will be calculated as  $\frac{100 * \text{actual dose}}{\text{planned dose}}$

All information will be listed. Also subjects out of the treatment compliance range of 80-120 % will be listed.

### 6.2 Concomitant medication

Concomitant medication is recorded at baseline and during the trial.

Sponsor: Pharmacosmos A/S	Date: 12MAR2018	
Drug/Project: Monofer	Version: Final 2.0	
Trials: P-Monofer-IDA-04 P-Monofer-IDA-05	Statistical Analysis Plan	

Concomitant medication will be summarised and will also listed by subject. Subjects using prohibited medication during the trials will be listed.

## 7 Statistical Methodology

The safety analysis set will be used for all safety endpoints and the ITT analysis set will be used for all efficacy endpoints if nothing else is stated.

### 7.1 Analysis and Presentation of the Primary Endpoint

The primary endpoint is

- Incidence of hypophosphatemia, defined as *s*-phosphate < 2 mg/dL, at any time from baseline to day 35.

#### 7.1.1 Incidence of hypophosphatemia at any time from baseline to day 35

The incidence of hypophosphatemia at any time from baseline to day 35 will be tabulated and exact 95 % CI will be estimated for each treatment group.

Iron isomaltoside will be compared to ferric carboxymaltose by CMH as described in section 5.1.1..

Two sensitivity analyses will be presented:

- The treatment groups will be compared by a logistic regression model with treatment and strata as factors and baseline *s*-phosphate as covariate. The estimated treatment ratio of iron isomaltoside versus ferric carboxymaltose will be presented with 95 % CIs and corresponding p-value.
- The treatment groups will also be compared by Fisher's exact tests where the p-value will be presented

All subjects in the safety analysis set will be included in the analyses.

If very few subjects are present in one of the strata, similar analyses will be presented, but where two of the categories are grouped.

The number and percentage of subjects with hypophosphatemia will be presented by treatment and visit, and by treatment, strata and visit using bar chart. The *s*-phosphate data will be listed by subject. Subjects with *s*-phosphate < 2 mg/dL will be listed.

### 7.2 Analysis and Presentation of the Secondary Safety Endpoints

The secondary safety endpoints are the following:

- Incidence of *s*-phosphate < 1.0 mg/dL at any time from baseline to day 35
- Time with hypophosphatemia (i.e. time with *s*-phosphate < 2.0 mg/dL) from baseline to day 35
- Proportion of hypophosphatemia at day 35
- Absolute [Δ] and relative [%] changes in *s*-phosphate from baseline to day 1, 7, 8, 14, 21, and 35
- Fractional phosphate urinary excretion at day 1, 7, 8, 14, 21, and 35
- Change in iFGF23, cFGF23, vitamin D (25, 1.25, 24.25), PTH, and ionized calcium from baseline to day 1, 7, 8, 14, 21, and 35
- Type and incidence of AEs
- Serious or severe hypersensitivity reaction starting on or after the first dose of randomized treatment (i.e. treatment emergent). The hypersensitivity terms are defined as standardised Medical Dictionary for Regulatory Activities query (SMQ) terms (including four additional terms) in the protocol in Appendix A.

Sponsor:	Pharmacosmos A/S	Date:	12MAR2018
Drug/Project:	Monofer	Version:	Final 2.0
Trials:	P-Monofer-IDA-04 P-Monofer-IDA-05		Statistical Analysis Plan

### 7.2.1 Incidence of s-phosphate < 1.0 mg/dL at any time from baseline to day 35

The incidence of s-phosphate < 1.0 mg/dL at any time from baseline to day 35 will be analysed and presented like the primary endpoint using CMH as described in section 5.1.1 and the sensitivity analyses described in section 7.1.1.

The number and percentage of subjects with s-phosphate < 1.0 mg/dL will be summarised by treatment and day. The s-phosphate data will be listed by subject as mentioned in section 7.1.1.

### 7.2.2 Time with hypophosphatemia from baseline to day 35

The time with s-hypophosphatemia will be calculated as the actual number of days from the first day where s-phosphate < 2 mg/dL until the first day where s-phosphate ≥ 2 mg/dL. If the subject does not reach s-phosphate ≥ 2 mg/dL then it will be treated as censored at day 35. If a subject experiences more than one period with s-phosphate < 2 mg/dL, the longest period will be used in the analysis.

The time with hypophosphatemia from baseline to day 35 will be presented by a Kaplan-Meier plot. The treatment groups will be compared by a log-rank test. Only subjects who have one or more s-phosphate value(s) < 2 mg/dL will be included.

Plots including the Kaplan-Meier curves, log-rank test and median time with hypophosphatemia will be presented overall by treatment. All periods will be presented by subject in a swimmer plot.

### 7.2.3 Proportion of hypophosphatemia at day 35

The proportion of subjects with hypophosphatemia at day 35 will be analysed and presented like the primary endpoint using the CMH described in section 5.1.1. for observed cases only.

The number and percentage of subjects with hypophosphatemia will be summarised by treatment and listed by subject as described in section 7.1.1.

### 7.2.4 Absolute [Δ] and relative [%] changes in s-phosphate from baseline to day 1, 7, 8, 14, 21, and 35

The change in s-phosphate from baseline to day 1, 7, 8, 14, 21, and 35 will be analysed and presented using the MMRM described in section 5.1.1.

The change in s-phosphate will be summarised by treatment and visit, and mean plot of absolute change over time will be presented.

The percentage change in s-phosphate from baseline to day 1, 7, 8, 14, 21, and 35 will be analysed and presented using the MMRM described in section 5.1.1.

The percentage change in s-phosphate will be summarised by treatment and visit, and mean plot of percentage change over time will be presented.

### 7.2.5 Fractional phosphate urinary excretion at day 1, 7, 8, 14, 21, and 35

The fractional phosphate urinary excretion at day 1, 7, 8, 14, 21, and 35 including change from baseline will be summarised by treatment and visit. All data will be listed by subject.

Sponsor: Pharmacosmos A/S	Date: 12MAR2018	
Drug/Project: Monofer	Version: Final 2.0	
Trials: P-Monofer-IDA-04 P-Monofer-IDA-05	Statistical Analysis Plan	

## 7.2.6 Change in iFGF23, cFGF23, vitamin D (25, 1.25, 24.25), PTH, and ionized calcium from baseline to day 1, 7, 8, 14, 21, and 35

The change in each of the following 7 endpoints

- iFGF23
- cFGF23
- vitamin D (25)
- vitamin D (1.25)
- vitamin D (24.25)
- PTH
- ionized calcium

from baseline to day 1, 7, 8, 14, 21, and 35 will be analysed using the MMRM described in section 5.1.1..

A summary of absolute values and change from baseline by treatment and visit, and mean plots of change over time will be presented for each endpoint. All data will be listed by subject.

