**Table 2 Visit schedule**

Visit	1 Screening	2 Baseline	3	4	5	6	7	8
Time (days)	Max -28	0	1	7	8	14	21	35
Visit window (days)	-	-	+ 1	+ 1	+ 1	± 2	± 3	± 3

The visits will be labelled by screening, baseline and scheduled day. Categorical data will be summarized by treatment, using number and percentages of subjects. For calculation of percentages, the denominator will either be the number of subjects in the analysis set or the number of subjects in the analysis set with non-missing values. Continuous data will be presented using the number of subjects (n), mean, standard deviation (SD), median, lower quartile, upper quartile, minimum and maximum. Both the absolute values and the change from baseline will be presented.

Sponsor:	Pharmacosmos A/S
Drug/Project:	Monofer
Trials:	P-Monofer-IDA-04 P-Monofer-IDA-05

Date:	12MAR2018
Version:	Final 2.0
Statistical Analysis Plan	

Descriptive statistics for all endpoints will be presented by treatment group and day, if applicable, using observed cases, i.e. no imputation of missing data will be performed. Missing data for time to event endpoints is handled using censoring.

Values below lower limit of quantification (LLOQ) will be substituted by 0.5\*LLOQ in tables and figures.

In the following, strata are defined as *Type of underlying disease: women with IDA due to gynaecological blood losses (yes or no) and screening s-phosphate level (< 3.5 mg/dL or ≥ 3.5 mg/dL)*.

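### SAP 7.2.2 censors every unresolved subject at day 35, so those who withdraw while low gain unobserved risk time; for completers the meaning of day 35 is ambiguous

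*SAP*

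**What the plan says.** SAP 7.2.2 measures the duration on the scale of actual days: it is "calculated as the actual number of days from the first day where s-phosphate < 2 mg/dL until the first day where s-phosphate ≥ 2 mg/dL". For subjects not seen to recover it gives a single instruction: "If the subject does not reach s-phosphate ≥ 2 mg/dL then it will be treated as censored at day 35". Only subjects with at least one value below 2 mg/dL enter the analysis. The outputs are a Kaplan-Meier plot with the median, and a test: "The treatment groups will be compared by a log-rank test".

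The only other text on censoring is a general line in SAP 5.1, below Table 2: "Missing data for time to event endpoints is handled using censoring". It names no date. Section 7.6 (missing values) adds nothing for this endpoint, and section 8 changes only how the periods are displayed.

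Table 2 allows visit 8 to fall 3 days either side of day 35, so on days 32 to 38. Section 5.1 also says that visits are labelled by their scheduled day.

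**The concern.** Kaplan-Meier and log-rank methods assume that a subject counted at risk is still under observation. A subject who leaves while low, and is then kept at risk until day 35, supplies risk time in which no recovery could have been recorded. This raises the estimated share still low and lengthens the apparent duration. If withdrawal differs between arms, it can also produce a difference in the log-rank test where there is none in duration.

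The second point concerns completers. If day 35 is the nominal day, recoveries are timed by actual date and censoring by schedule. A recovery found on day 38 would then be counted after still-low subjects with the same onset had already left the risk set, and the curve could fall to 0 % although they never recovered.

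**Working it through.** The SAP states no figure for this endpoint, and no withdrawal rate, onset pattern or recovery pattern. All inputs below are assumptions, except the visit days and windows (Table 2) and the group sizes. From SAP 3.3.1, 60 per group with incidences of 40 % and 15 % give 24 and 9 affected subjects.

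**Unobserved days added.** For a subject last sampled low on day L, the rule adds 35 − L days. For L = 1, 7, 8, 14 and 21 this is 34, 28, 27, 21 and 14 days. First low at day 7 and last low at day 14: observed 14 − 7 = 7 days, credited 35 − 7 = 28 days.

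**Kaplan-Meier illustration.** 24 affected, all first low at day 7; 6, 7 and 4 recover at days 14, 21 and 35 (durations 7, 14 and 28 days). Of the 7 not seen to recover, W withdraw after the day 14 sample. At each recovery time, S is multiplied by (1 − recoveries / number at risk).

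- As written, for any W: 18/24 = 0.750 at 7 days, × 11/18 = 0.458 at 14 days, × 7/11 = 0.292 at 28 days.
- Last-sample censoring removes the W subjects from the risk set after 7 days:

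| W | S at 14 days | S at 28 days |
|---|---|---|
| 1 | 0.750 × 10/17 = 0.441 | × 6/10 = 0.265 |
| 2 | 0.750 × 9/16 = 0.422 | × 5/9 = 0.234 |
| 3 | 0.750 × 8/15 = 0.400 | × 4/8 = 0.200 |
| 4 | 0.750 × 7/14 = 0.375 | × 3/7 = 0.161 |

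The median is 14 days under both rules.

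**Median under slower recovery.** With 5, 6 and 5 recoveries and 8 unresolved, S at 14 days is 13/24 = 0.542 as written (median 28 days). With last-sample censoring it is 0.528, 0.512, 0.495 and 0.475 for W = 1 to 4, so the median stays at 28 for W = 1 or 2 and becomes 14 for W = 3 or 4. In a large-sample simulation (onset at day 7, 8 or 14, exponential recovery with a true median of 14 days, visits spread over their windows), the estimated median at 0, 10, 20 and 30 % dropout was 22, 23, 24 and 26 days as written, against 22, 22, 21 and 21.

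**Log-rank test, no true difference in duration, nominal 5 %.** 24 v 9 affected, recovery as in the first illustration, withdrawal after day 14 as a share of all affected:

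| Withdrawal | As written | Last sample |
|---|---|---|
| None | 5.4 % | 5.4 % |
| 4 %, larger arm only | 5.7 % | 5.6 % |
| 17 %, both arms | 5.4 % | 5.3 % |
| 17 %, larger arm only | 7.6 % | 5.6 % |

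Under the large-sample simulation's assumptions, dropout of 20 % in the larger arm and 5 % in the smaller gave 7.2 % v 4.9 %; 30 % v none gave 11.8 % v 5.0 %.

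**Completers, if day 35 is nominal.** First illustration, no withdrawal, 3 of the last 4 recoveries on day 35 and 1 on day 38, with 7 subjects still low on day 38. As written: 11/24 × 8/11 = 0.333 at 28 days; the 7 are then censored at 28, one subject remains, and S = 0 at 31 days. With last-sample censoring: 0.333 × 7/8 = 0.292 at 31 days, which is the true 7/24. With visit 8 uniform over days 32 to 38, the curve ended at 0 % with someone still low in 83 % of simulated arms as written, against 20 % with last-sample censoring. With only 10 % of these visits late, it was 33 % against 22 %. The log-rank rejection rate was 5.4 % under both rules.

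**The case against.** **Last-sample censoring was meant.** Time with hypophosphatemia is the only endpoint in the SAP analysed by Kaplan-Meier and log-rank, so the general line in 5.1 must refer to it, and the day 35 sentence could be meant for subjects followed to the end. This is plausible, but 7.2.2 makes no such distinction and 5.1 gives no date. A programmer working from the final text would apply day 35 to everyone.

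**Day 35 is the name of visit 8.** This objection largely stands. Section 5.1 labels visits by scheduled day, 7.2.3 uses day 35 in that sense, and 7.2.2 counts in actual days. A reader might infer that completers are certainly censored on the wrong date. The SAP does not support that: if the actual date of visit 8 is meant, the problem does not arise. It is an ambiguity to settle.

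**The worst case may be deliberate.** Section 7.6 counts subjects without post-baseline s-phosphate as low in the primary analysis, and carrying subjects to day 35 has a similar flavour. The SAP states no such purpose for this endpoint.

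**The effect is small and would be seen.** Much of this stands. The 16.1 % figure needs 4 of the 7 unresolved subjects to have withdrawn, and the median shift in the worked example arises because the estimate there lies close to 0.5. The swimmer plot shows every period by subject, and 7.2.3 reports the day 35 proportion from observed cases, so a misleading curve end would be open to challenge. Section 5.2 does list "Lost to follow-up" as a withdrawal reason, but in a generic list; it does not predict losses among subjects who are low.

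**Conclusion.** The concern holds in a limited form. As written, 7.2.2 keeps subjects who withdraw while low at risk for days on which they were not observed, and this lengthens the Kaplan-Meier estimate of duration. In the illustration the share still low at 28 days is overstated by 2.7 percentage points with 1 of 24 withdrawn (29.2 − 26.5) and by 13.1 with 4 of 24 (29.2 − 16.1). The median seldom moves when withdrawal is rare; it can lengthen when withdrawal is heavy.

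A reader might infer that the log-rank comparison is generally invalid. The calculations do not show that: with rare or balanced withdrawal its error rate is essentially the same under both rules, and it rises only when withdrawal is clearly unequal between arms. For completers, the finding is that day 35 is undefined, with a consequence under the nominal reading only.

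Every magnitude rests on assumed onset, recovery, withdrawal and visit timing. The endpoint is a secondary safety endpoint without multiplicity adjustment (7.7), and the primary analysis does not use this rule. The weight is modest, but the correction is worth making.

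**What to change.** In SAP 7.2.2, replace the censoring sentence by: a subject whose hypophosphatemia is not seen to resolve is censored at the actual date of the last available s-phosphate sample, whether at visit 8 or earlier. This settles both points, because events and censoring then run on the same clock. If carrying subjects to day 35 is wanted as a worst case, keep it as a named sensitivity analysis.

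The cost is one sentence and one derivation, with no new data. Three limits remain. A subject whose first low value is also the last sample contributes 0 days. Last-sample censoring assumes that withdrawal is unrelated to duration, which the day 35 sensitivity analysis would help to probe. The end of the curve stays unstable with few at risk: it still reached 0 % in about 20 % of the simulated arms.

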##### 3.1.2 Secondary safety objectives

The secondary safety objectives of the trials are to compare the effects of iron isomaltoside and ferric carboxymaltose treatment in subjects with IDA on the following:

- (1) Incidence of severe hypophosphatemia
- (2) Time with hypophosphatemia
- (3) Proportion of subjects with hypophosphatemia at the last visit
- (4) Absolute [Δ] and relative [%] changes in serum-phosphate (s-phosphate)
- (5) Fractional phosphate urinary excretion
- (6) Intact Fibroblast Growth Factor 23 (iFGF23), C-terminal FGF23 (cFGF23), vitamin D (25, 1.25, 24.25), Parathyroid Hormone (PTH), and ionized calcium
- (7) Adverse Events (AEs) and biochemical safety parameters

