### 3.3 Subject included

#### 3.3.1 Sample Size Determination

Data from a previous trial conducted with iron isomaltoside 1000 mg suggests that the incidence of hypophosphatemia in a gynaecology population with/without heavy uterine bleeding can be expected to be approximately 10 % (P-Monofer-IDA-01, 1000 mg; n=3/29=10.3 %, 95 % Confidence Interval (CI) = 2-27 %, gynaecology subgroup; n = 1/10 = 10.0 %, 95 % CI = 0-45 %). For ferric carboxymaltose, the incidence has been observed to be 40-70 % (e.g. Wolf *et al.*, 2013; n = 10/17 = 59 %, 95 % CI = 33-82 %). The significance level is set to 5 %, and the power is set to 80 %. Assuming incidences of 15 % for iron isomaltoside and 40 % for ferric carboxymaltose, 49 subjects in each treatment group is required to detect a difference between the treatment groups.

To account for the uncertainty, and to gain more safety information, 60 subjects per treatment group will be randomized in both trials.

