## 7.6 Handling of Missing Values

For the primary endpoint, the first post-baseline s-phosphate measurement is taken at day 1, hence, very few missing values are expected. If there are subject(s), for whom no post-baseline s-phosphate

Sponsor:	Pharmacosmos A/S	Date:	12MAR2018
Drug/Project:	Monofer	Version:	Final 2.0
Trials:	P-Monofer-IDA-04 P-Monofer-IDA-05	Statistical Analysis Plan	

measurement(s) are available, these subjects will be set as having s-phosphate < 2 mg/dL in the primary analysis.

In the MMRM analyses subjects without post-baseline values will have change from baseline set to 0 at the first post-baseline visit.

Missing values for the SF-36 questionnaires will be handled using the Half-scale rule, i.e. a score will be calculated if at least 50 % of the items are answered by a subject at a given visit. The missing items will be imputed by the average score of the non-missing items. The PCS score can be computed if at least seven scales have been scored, one of which being the PF scale; similarly, the MCS score can be computed if at least seven scales have been scored, one of which being the MH scale.

Besides from this no imputation of missing values will be applied.

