## 7.10 Combined Analysis of P-Monofer-IDA-04 and P-Monofer-IDA-05

The two trials P-Monofer-IDA-04 and P-Monofer-IDA-05 is planned to run in parallel and the same dosing regimens are investigated.

Pooled analyses of primary and secondary safety and efficacy endpoints will be performed for the two trials.

The analyses will be performed similar to those specified for the individual trials, with the addition of trial in the models, i.e. the CMH method will be stratified by strata and trial and the MMRM will include the fixed, categorical effects of trial, treatment, strata, day, treatment-by-day interaction. Also, the overall incidence of TEAEs and ADRs will be compared between the treatment groups using Fisher's Exact test.

The CSRs will be finalised without the combined analyses, which will be done when both trials are finalised. The combined analysis will be included as an appendix to the CSRs.

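### Time with hypophosphatemia is compared only among affected subjects, so days below 2 mg/dL are never compared between the randomised groups, and subjects who withdraw while low are censored too late

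*SAP*

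**What the plan says.** SAP section 3.1.2 sets the aim: "The secondary safety objectives of the trials are to compare the effects of iron isomaltoside and ferric carboxymaltose treatment" in subjects with IDA, and time with hypophosphatemia is item 2 of that list. Section 7.2 defines the endpoint as the time with s-phosphate below 2.0 mg/dL between baseline and day 35.

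Section 7.2.2 then defines the analysis:

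- The clock starts at the first value below 2 mg/dL and stops at the first value of 2 mg/dL or more. With several periods, "the longest period will be used in the analysis".
- If 2 mg/dL is not reached, "then it will be treated as censored at day 35". Withdrawal is not mentioned.
- The groups are compared by log-rank, and "Only subjects who have one or more s-phosphate value(s) < 2 mg/dL will be included".
- For output, "Plots including the Kaplan-Meier curves, log-rank test and median time with hypophosphatemia will be presented overall by treatment". The swimmer plot of all periods is descriptive.

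Section 5.1 adds that missing time-to-event data are handled by censoring, without giving a censoring time. Section 7.10 carries the methods into the combined analysis: "Pooled analyses of primary and secondary safety and efficacy endpoints will be performed for the two trials".

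**The concern.** **Who is compared.** Having a value below 2 mg/dL is the primary endpoint itself and is observed after randomisation. Subjects who become low on one drug need not resemble those who become low on the other, so randomisation does not protect a comparison between them. The test answers a legitimate question, namely how quickly affected subjects recover. The stated objective is different: how much time subjects given each drug spend below 2 mg/dL. No other inferential analysis addresses it. The p-value shown beside the Kaplan-Meier curves and medians is therefore likely to be read as the treatment comparison of time with hypophosphatemia. It can be null when the arms differ greatly in days low, or point against the arm with fewer days low.

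**When censoring occurs.** Day 35 is right for a subject still low at the last visit. For a subject who leaves while low, it treats the days after the last measurement as observed non-recovery. This raises the late part of the Kaplan-Meier curve.

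The stake is one named secondary safety endpoint, in each trial and in the combined analysis. The primary conclusion does not depend on it.

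**Working it through.** **Inputs from the SAP.** Section 3.3.1: "Assuming incidences of 15 % for iron isomaltoside and 40 % for ferric carboxymaltose", 5% significance, 80% power, 49 per group required, 60 per group randomised. Visits are on days 1, 7, 8, 14, 21 and 35. The SAP gives no durations among cases and no withdrawal rate, so those below are assumptions, shown over a range.

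**The plan's own figure.** The two-proportion formula with pooled variance, two-sided 5% and 80% power gives 49 per group for 15% v 40%, as stated. Power is 80.1% at 49 and 87.6% at 60.

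**Subjects entering the log-rank.** 60 × 0.15 = 9 and 60 × 0.40 = 24. Pooled over both trials: 18 and 48.

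**Equal durations among cases.** Take exponential durations with mean m, capped at 28 days (onset day 7 to day 35). Mean days low per case is m(1 − e^(−28/m)); multiplying by incidence gives days per treated subject. Section 7.2.2 counts to the visit at which recovery is seen. With onset at day 7, the possible counts are 1, 7, 14 and 28 days, and the mean per case is 1 + 6e^(−1/m) + 7e^(−7/m) + 14e^(−14/m).

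| m (days) | Per case, continuous | Per subject, 15% v 40% | Per case, visit days | Per subject, 15% v 40% |
|---|---|---|---|---|
| 7 | 6.87 | 1.0 v 2.7 | 10.67 | 1.6 v 4.3 |
| 14 | 12.11 | 1.8 v 4.8 | 15.98 | 2.4 v 6.4 |
| 28 | 17.70 | 2.7 v 7.1 | 20.73 | 3.1 v 8.3 |

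The ratio is 0.40/0.15 = 2.7 in every row, and the log-rank null is true in every row. In 2000 simulated trials with continuous durations the log-rank rejected in 7.4%, 6.7% and 5.3%. That is roughly its nominal size, not lost power.

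**Longer durations in the lower-incidence arm.** With mean 28 days in the 15% arm and 14 in the 40% arm, days per subject are 0.15 × 17.70 = 2.7 v 0.40 × 12.11 = 4.8 (3.1 v 6.4 on visit days). The log-rank rejected in 29% of single trials and 56% of pooled analyses. A repeat gave 30% and 55%, with nearly all rejections against the 15% arm; on visit days it gave 30% and 53%.

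**Why the log-rank should stay.** With 40% incidence in both arms and durations of 7 v 14 days, the cases-only log-rank rejects in 61.5%, and an all-subject Wilcoxon test in 10.0%. At 15% v 40% with equal durations, that Wilcoxon gives the same verdict as a chi-square test on incidence in 96-97% of trials. A rank test alone would therefore mostly repeat the primary analysis.

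**Censoring.** A subject low at day 7, still low at day 14 and then withdrawn has 14 − 7 = 7 days observed and 35 − 7 = 28 entered. For the curve, take onset at day 7, mean 14 days, and probability w of withdrawing after each of the low visits on days 8, 14 and 21. With S(t) = e^(−t/14):

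- Withdrawn while low: W = wS(1) + w(1−w)S(7) + w(1−w)²S(14).
- Kaplan-Meier at 28 days under the day-35 rule: W + (1−w)³S(28).
- Correct value: S(28) = 0.14, which censoring at the last measurement recovers.

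| w | Cases withdrawn while low | Day-35 rule | Last measurement |
|---|---|---|---|
| 3% | 0.028 + 0.018 + 0.010 = 5.6% | 0.18 | 0.14 |
| 6% | 0.056 + 0.034 + 0.020 = 11.0% | 0.22 | 0.14 |
| 10% | 0.093 + 0.055 + 0.030 = 17.7% | 0.28 | 0.14 |

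The median is 14 days under both rules here. Under heavier and earlier withdrawal (20% of cases, leaving at or just after onset), a separate simulation moved the day-35 median from 14 to 21 days.

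**The case against.** **The restriction is written in plain sight, and recovery among cases is a valid question.** Both are true, and the analysis should be kept. But the endpoint and its objective are stated without the restriction, and the output is described as an overall presentation by treatment. Nothing says that the p-value does not answer the objective.

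**All-subject information exists elsewhere.** The SAP compares incidence below 2 and below 1 mg/dL, the proportion low at day 35 in observed cases, and change in s-phosphate at every visit. None of these measures days low. Still, with equal durations the 2.7-fold difference is simply 40% over 15%, which the primary analysis already tests. That stands: most of an all-subject difference would come from incidence. The gap matters most when recovery differs between arms, and nothing in the SAP says that it will.

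**Continuous durations do not follow the SAP's definition.** Correct. Visit-day counts are higher, which is why both are tabulated. The ratio and direction do not change.

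**The censoring sentence may be meant only for completers, and few subjects are affected.** The general sentence in section 5.1 names no time, so it does not override the explicit day-35 rule. The number affected may well be small: 5.6% to 17.7% of 9 and 24 cases is about 0.5 to 1.6 and 1.3 to 4.2 subjects. This is the lesser point.

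**Conclusion.** Both parts hold on the SAP's text.

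The only planned comparison of time with hypophosphatemia conditions on the primary outcome and does not address the objective as written. The 2.7-fold ratio at equal durations follows from the SAP's own incidences whatever the common duration. The numbers of days, and the roughly 30% (pooled 55%) rejection in the adverse direction, rest on assumed durations.

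The censoring rule is wrong for a subject who withdraws while low. Its effect on the 28-day Kaplan-Meier estimate is 0.04 to 0.14 over the assumed withdrawal range. No general effect on the log-rank is claimed, since that depends on how withdrawal while low differs between arms.

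This should be corrected before analysis. It does not touch the primary conclusion.

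**What to change.** 1. **Add an all-subject comparison.** In the safety analysis set, compare days below 2 mg/dL up to day 35, with 0 days for subjects never low. Report the difference in mean days with a 95% CI, adjusted for the randomisation strata, by a method that allows for early withdrawal. State whether total days or the longest period is used. State also how a subject with no post-baseline s-phosphate is handled: section 7.6 says "these subjects will be set as having s-phosphate < 2 mg/dL in the primary analysis" but gives no rule for duration. One workable estimator for total days sums, over visits, the proportion low times the days to the next visit, weighted for the probability of still being observed, with a bootstrap CI. In a 500-trial check (onset at days 7-21, SAP visits, withdrawal per visit 2% if not low and 6% if low), true differences of 2.96, 3.91 and 4.61 days were estimated as 2.95, 3.83 and 4.56, with coverage of 93%, 95% and 93%. That check was unstratified, so the stratified version needs its own. A rank test may be added but should not be the only measure.
2. **Label the existing analysis.** Keep the cases-only Kaplan-Meier curves, medians and log-rank, described as conditional on having hypophosphatemia and not a randomised comparison.
3. **Correct the censoring time.** Censor a non-recovered subject at the last available s-phosphate measurement.

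Apply all three to the combined analysis in section 7.10. The cost is SAP wording and one more table from data already collected. The drawback is partial overlap with the incidence endpoint, which should be acknowledged when the result is reported.
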